5.1 General, demographic and baseline characteristics

Age (years)

The age will not be recalculated. The values automatically derived in the CRF will be used in the analysis.

Body Mass Index (BMI) (kg/m2)

BMI will not be recalculated. The values automatically derived in the CRF will be used in the analysis.

Previous and Concomitant Medication

Any medication the subject takes from the signature of informed consent and through the duration of the study, other than the study drug, is considered a concomitant medication.

The CRF records all concomitant medications and all medications taken within 30 days prior to Screening.

The medications labelled as 'ongoing' in the 'Prior and Concomitant Medications and Procedures' page in the eCRF will be considered concomitant medications. All other medications are evaluated based on the date: all records with start or end date after the date of signature of the informed consent are labelled as concomitant, other medications are labelled as past.

Past and Concomitant disease

Medical history will be recorded in the CRF. A disease is concomitant if ongoing at Screening visit (i.e. it ended after Screening visit).

A disease is considered as past if it ended prior to the Screening visit.

The diseases labelled as 'ongoing' in the 'Medical and Surgical procedure history' page in the eCRF will be considered concomitant diseases, all other diseases will be defined as past.

Study drug intake

Each dispensing of study drug will be documented in the eCRF.

Date of first randomised study drug intake is the Study Visit 2 date, at which the trial drug is dispensed.

Date of last randomised study drug intake is the date of study visit 6. If this date is missing, the last Study Visit date available will be considered (excluding Visit 1 and Visit 7 dates). The tapering period will not be included to assess the last intake.

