 - Herbal preparations (other than St John's wort mentioned above). However, subjects who have been on a stable dose of these preparations prior to entering the study may continue to take these drugs. No new herbal preparations may be introduced or dosage changes initiated while participating in the study.
5. Days outside the protocol timeframe (protocol allowed time window is ± 2 days) at Visit 6 greater or equal to 8 days will be considered a major protocol deviation. If the number of days outside the protocol timeframe is smaller or equal to 7 the deviation is considered minor.

5. Definitions and Data Conventions

This section contains definitions and conventions that will be used for analysis.

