5.2 Compliance

All subjects will enter the Screening Placebo Run-In Period (2 weeks) during which they will receive the placebo treatment twice daily.

After randomisation, subjects are instructed to take the study drug or the matched Placebo orally twice daily (BID) for 8 weeks. Study treatment (litoxetine or placebo) will be provided with dose titration, starting with 10 mg BID for 1 week, escalated to 20 mg BID for 1 week, and subsequently escalated to 30 mg BID for 6 weeks for a total litoxetine treatment duration of 8 weeks.

After 8 weeks of treatment, doses will be reduced by 50% over 1 week to taper off treatment.

Compliance will be computed for treatment period only, ie. from Visit 2 to Visit 6 (8 weeks).

During the treatment period, patients are instructed to take two capsules in the morning and two capsules in the evening. The two capsules will be taken as follows: one from jar A and one from jar B.

The CRF captures the actual medication taken based on quantitative pill count at the site. The CRF data is therefore to be used as the source to determine patient treatment compliance.

The Investigational Site personnel will collect the study drug containers and will count and record unused study drug. This information will be used to compute compliance according to the following formula:

$$\text{Compliance} = \left(\frac{\text{Total number of Capsules taken}}{\text{Number of days between Visit 2 and Last study drug intake} \times 4} \right) \times 100$$

The above formula takes into account the fact that four capsules are taken each day (number of days \times 4).

If the date of last study drug intake is not available, the date of the latest available visit will be considered in the formula above (excluding Visit 1 and Visit 7 dates).

To compute the compliance for Jar A and Jar B separately, the following formula will be used:

$$\text{Compliance Jar } i = \left(\frac{\text{Total number of Capsules taken from Jar } i}{\text{Number of days between Visit 2 and Last study intake} \times 2} \right) \times 100$$

Where $i = A, B$.

The formula takes into account that two capsules from each Jar are taken at each day.

The total number of capsules taken during the treatment period will be derived from the eCRF as:

$$\text{Capsules taken} = \text{capsules dispensed} - \text{capsules returned} - \text{capsules not taken/not returned}$$

Treatment duration will be calculated as:

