$$\text{Treatment Duration} = \text{Date of last study drug intake} - \text{Date of first drug intake}$$

The date of the first study drug intake is the date of Visit 2, after randomisation to treatment (it excludes the Placebo Run-in period). Date of last randomised study drug intake is the date of Study Visit 6. If this date is missing, the date of last Study Visit available will be considered (excluding Visit 1 and Visit 7 dates).

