6.8 Additional Safety Analyses

Adverse Events

The number of treatment-emergent AEs, non-TEAEs, AEs occurring during follow-up or following discontinuation, AEs leading to death, AEs leading to discontinuation and SAEs, and the number and the percentage of patients experiencing those events, will be summarised by treatment group. Differences between groups will be evaluated using Chi-square test or Fisher's exact test (if more than 20% of the cells in a contingency table have counts less than 5).

The following adverse events will be specifically summarized by treatment:

1. TEAEs of Special Interest include urinary retention, psychiatric adverse events (nervousness, anxiety, panic attacks, insomnia, aggression, mania, suicidal ideation, development/worsening of depression) and withdrawal symptoms
2. Treatment Emergent Suicidal Adverse Events and Adverse Events suggestive of abuse potential
3. SAEs
4. TEAEs
5. Non-TEAEs
6. AEs/SAEs which occurred during the 30-day Follow-up Period or following discontinuation

The SOCs and PTs will be used for tabulation. The number of AEs and the number and the percentage of patients with at least one AE will be presented by SOC and PT for each treatment group. Within each SOC and PT, the highest severity grade attained will be reported, for AEs with divergent severities.

A comparison of treatment-emergent AE rates between lítoxetine and placebo will be performed using an exact logistic regression model with the treatment-emergent AE ("1"=At least one treatment-emergent AE occurred for the patient; "0"=otherwise) as dependent variable and lítoxetine dose as fixed effects. The probability modelled will be treatment-emergent AE="1".

The number of patients and the number of patients considered in the model will be provided. The exact odds ratio of the fixed effects will be calculated as the number of patients with/without AEs in all arms. If the omnibus test is significant, comparisons between arms will be tested individually, with the relative 95% CI and p-value.

The same model will be repeated by considering SAE ("1"=At least one SAE occurred for the patient; "0"=otherwise) as dependent variable.

AEs leading to study drug discontinuation and AEs leading to death will be presented in the listings only.

SAEs will be listed and summarised in a table, including a description of each event, the time to onset, the severity, and the relationship to trial drug.

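### The last randomised dose is dated by a clinic visit rather than the actual stop: treatment duration is misstated, taper exposure goes unreported, and the post-discontinuation adverse-event period has no defined start

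*SAP*

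**What the plan says.** - **Last dose.** SAP 5.1: "Date of last randomised study drug intake is the date of study visit 6". If Visit 6 has no date, the latest attended visit is used, never Visit 1 or Visit 7. SAP 5.2 repeats the rule for treatment duration: "Date of last randomised study drug intake is the date of Study Visit 6".
- **Taper.** SAP 5.1: "The tapering period will not be included to assess the last intake". SAP 5.2 describes the taper itself: "After 8 weeks of treatment, doses will be reduced by 50% over 1 week to taper off treatment".
- **Compliance.** SAP 5.2 divides capsules taken (by pill count) by four times the days from Visit 2 to last intake, and adds: "If the date of last study drug intake is not available, the date of the latest available visit will be considered". Compliance is confined to Visit 2 to Visit 6. Protocol 8.6 sets the 80% criterion over the Treatment Period, and SAP 4.3 lists compliance below 80% as a deviation.
- **Adverse events after stopping.** SAP 6.8, item 6, tabulates "AEs/SAEs which occurred during the 30-day Follow-up Period or following discontinuation" and gives no start date.
- **Schedule (protocol Appendix 2).** Visits 2 to 7 fall on Days 14, 21, 28, 35, 70 and 105. Between Visit 5 and Visit 6 there is only a telephone contact on Day 42, for the suicidality scale. Visit 6 is also the early termination visit.

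**The concern.** The day on which a subject stopped taking capsules does not enter the last-dose rule in SAP 5.1. In a trial whose primary objective is safety and tolerability, the exposure summary should say how long subjects took the drug. The reported duration is instead the time to a clinic visit, and the schedule leaves five weeks without one.

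Withdrawal symptoms are a named event of interest, and protocol 4.3 expects them mostly within days of stopping. To read them, one must know which events fell in full-dose treatment, in the half-dose taper week, and off drug. The SAP does not define those periods.

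The Per Protocol (PP) rules in SAP 4.1 and 4.3 set limits on the timing of Visit 6 ("If the number of days outside the protocol timeframe is smaller or equal to 7 the deviation is considered minor") but do not ask whether the Visit 6 diary week was spent on drug.

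**Working it through.** The documents give no stop dates, so the stop days below are assumptions. Days are counted from Visit 2, and every capsule is assumed taken up to the stop.

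**1. The plan's own figure.** Day 70 − Day 14 = 56 days = 8 weeks. 56 × 4 = 224 capsules. A completer who takes all of them has 224/224 = 100%. This reproduces.

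**2. Silent early stop, Visit 6 attended on day 56.**

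| Full days dosed | Duration reported | Excess (days) | Compliance, visit-date rule | Compliance, denominator ending at stop |
|---|---|---|---|---|
| 28 | 56 | 28 | 112/224 = 50.0% | 112/112 = 100% |
| 42 | 56 | 14 | 168/224 = 75.0% | 168/168 = 100% |
| 44 | 56 | 12 | 176/224 = 78.6% | 176/176 = 100% |
| 45 | 56 | 11 | 180/224 = 80.4% | 180/180 = 100% |
| 49 | 56 | 7 | 196/224 = 87.5% | 196/196 = 100% |

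The last two columns are the two wordings in the SAP. For the first three rows, the choice decides whether a compliance deviation is recorded.

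**3. Early stop with an early termination visit.** Stop on day 28, visit 3, 7 or 14 days later: duration is too long by 3, 7 or 14 days. Compliance is 112/124 = 90.3%, 112/140 = 80.0% or 112/168 = 66.7%.

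**4. Visit 6 missed, Visit 5 the last attended.** Reported duration is 35 − 14 = 21 days and the denominator is 84 capsules. With a true stop on day 28, 42 or 56, duration is too short by 7, 21 or 35 days. If those capsules are later counted as taken, compliance is 112/84 = 133%, 168/84 = 200% or 224/84 = 267%.

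**5. Taper in a completer.** 56 + 7 = 63 dosing days, of which 7/63 = 11.1% are not reported. On the full schedule the dose before taper is 20×7 + 40×7 + 60×42 = 2,940 mg. The taper adds 30×7 = 210 mg, and 210/3,150 = 6.7%.

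**6. Diary week.** The seven days before a day-56 Visit 6 begin on day 49. A subject with 45 to 49 full dosing days has 80.4% to 87.5% compliance and a diary filled in entirely after the last dose.

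**7. Start of the post-discontinuation table.** Counted from Visit 6, 30 days end on Day 100, before Visit 7 on Day 105. The taper ends on Day 77, which is 28 days before Visit 7; 30 days from there end on Day 107. The taper week is inside the first window and outside the second. The SAP does not choose between them.

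**The case against.** - **One rule, not two.** The fallback sentence in SAP 5.2 carries the same exclusion of Visits 1 and 7 as SAP 5.1, so it may be one visit-date rule loosely phrased. That would remove the inconsistency but not the error in duration.
- **Visit 6 doubles as the early termination visit.** This stands. For withdrawals who attend it, the error is only the gap in step 3.
- **Low compliance after an early stop is intended.** This stands in full. Ending the denominator at the stop date would score every early stopper 100% and defeat the 80% rule. Leaving the taper out of compliance is also legitimate. That an 80% threshold tolerates 11 missed days of 56 follows from the threshold, not from the last-dose rule.
- **Adverse events.** A reader might infer that on-drug and off-drug events are misclassified. The documents do not show that. Treatment-emergent status runs from Visit 2 to the follow-up visit (SAP 5.3). The dose-level bands in SAP 6.3 use visit dates, with footnotes for subjects off the protocol dosage. Neither uses the last-dose date, and nothing ties item 6 of SAP 6.8 to it. What remains is an undefined start.
- **Exposure as denominator.** A reader might also suppose that the primary safety rates are affected. They are proportions of subjects with Clopper-Pearson intervals (SAP 6.3, 6.7); duration is only summarised descriptively (SAP 6.6).

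**Conclusion.** The point holds for treatment duration. Followed as written, the rule overstates it by the gap from last capsule to Visit 6 or early termination. It understates it by up to 35 days when Visit 5 is the last visit attended and dosing went on beyond it. Compliance above 100% arises only in that second case, and only if the later capsules are counted as taken. Taper exposure is missing for completers too. The start of the post-discontinuation period, and the status of taper days within it, are undefined.

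The off-drug diary week is possible but narrower. It needs a subject who stops silently in about the last 7 to 11 days, stays in the study, and is otherwise eligible for PP.

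Treatment-emergent event counts and the primary safety proportions do not change. The number of subjects affected cannot be computed. Multiplying the 30% dropout by the 52 planned litoxetine subjects (two thirds of 78) gives 15.6, but the documents do not say how many dropouts stop between visits, and non-completers are outside PP anyway. Nor do they confirm that the eCRF holds a last-dose date for every subject.

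**What to change.** Amend SAP 5.1, 5.2 and 6.8 before unblinding:

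1. For treatment duration, use the actual stop date where the eCRF records it, with the visit date as fallback only. Align the wordings in 5.1 and 5.2.
2. Report taper exposure separately, with its own end date.
3. Start the table in SAP 6.8, item 6, from the actual stop date, and show taper-week events apart from off-drug events.
4. Keep the 80% compliance rule over the Treatment Period, Visit 2 to Visit 6, not cut off at the stop date. If Visit 6 is missing, the planned 8 weeks would serve: 168/224 = 75% in place of 200%.
5. At the blinded data review, flag subjects whose Visit 6 diary days fall after the last randomised dose, or exclude them from PP in a sensitivity analysis.

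The cost is SAP wording, at most one eCRF date if it is not already collected, and possibly a few fewer subjects in the PP analysis.

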5.2 Compliance

All subjects will enter the Screening Placebo Run-In Period (2 weeks) during which they will receive the placebo treatment twice daily.

After randomisation, subjects are instructed to take the study drug or the matched Placebo orally twice daily (BID) for 8 weeks. Study treatment (litoxetine or placebo) will be provided with dose titration, starting with 10 mg BID for 1 week, escalated to 20 mg BID for 1 week, and subsequently escalated to 30 mg BID for 6 weeks for a total litoxetine treatment duration of 8 weeks.

After 8 weeks of treatment, doses will be reduced by 50% over 1 week to taper off treatment.

Compliance will be computed for treatment period only, ie. from Visit 2 to Visit 6 (8 weeks).

During the treatment period, patients are instructed to take two capsules in the morning and two capsules in the evening. The two capsules will be taken as follows: one from jar A and one from jar B.

The CRF captures the actual medication taken based on quantitative pill count at the site. The CRF data is therefore to be used as the source to determine patient treatment compliance.

The Investigational Site personnel will collect the study drug containers and will count and record unused study drug. This information will be used to compute compliance according to the following formula:

$$\text{Compliance} = \left(\frac{\text{Total number of Capsules taken}}{\text{Number of days between Visit 2 and Last study drug intake} \times 4} \right) \times 100$$

The above formula takes into account the fact that four capsules are taken each day (number of days \times 4).

If the date of last study drug intake is not available, the date of the latest available visit will be considered in the formula above (excluding Visit 1 and Visit 7 dates).

To compute the compliance for Jar A and Jar B separately, the following formula will be used:

$$\text{Compliance Jar } i = \left(\frac{\text{Total number of Capsules taken from Jar } i}{\text{Number of days between Visit 2 and Last study intake} \times 2} \right) \times 100$$

Where $i = A, B$.

The formula takes into account that two capsules from each Jar are taken at each day.

The total number of capsules taken during the treatment period will be derived from the eCRF as:

$$\text{Capsules taken} = \text{capsules dispensed} - \text{capsules returned} - \text{capsules not taken/not returned}$$

Treatment duration will be calculated as:

$$\text{Treatment Duration} = \text{Date of last study drug intake} - \text{Date of first drug intake}$$

The date of the first study drug intake is the date of Visit 2, after randomisation to treatment (it excludes the Placebo Run-in period). Date of last randomised study drug intake is the date of Study Visit 6. If this date is missing, the date of last Study Visit available will be considered (excluding Visit 1 and Visit 7 dates).

5.3 Safety variables

All safety variables will be derived from the eCRF.

Adverse Event (AE) An AE is defined as any untoward medical occurrence in a patient or clinical investigation subject administered a pharmaceutical product and which does not necessarily have a causal relationship with this treatment.

Non-Treatment-Emergent Adverse Event (non-TEAE)

When an AE occurs after written consent has been obtained but before the first dose of treatment study drug (Visit 2 date), the AE will be considered a non-treatment emergent AE. Adverse Events, related to abnormal laboratory parameters, that were identified at Visit 2, when blood samples were collected before the first dose of the study drug, are considered non- TEAEs.

Treatment-Emergent Adverse Event (TEAE)

An AE that occurs from the time the subject receives his first dose of treatment study drug (Visit 2 date) until his last study visit (Follow-up Visit date) will be considered a treatment-emergent AE (TEAE) regardless of the assessed relationship to the administration of the study drug.

Immediately Reportable Adverse Event (IRAE)

Immediately reportable AEs (IRAEs) are AEs that must be reported to the Sponsor within 24 hours of the study site being informed of the IRAE.

Immediately reportable AEs include:

- All SAEs
- Overdose
- Pregnancy
- AEs that result in a subject's withdrawal from the study

For litoxetine in the current study and with the current posology, an overdose should be considered as any dose above 60 mg taken per day.

Serious Adverse Event (SAE)

A serious adverse event (SAE) is any untoward medical occurrence or effect that at any dose:

- Results in death
- Is life threatening
- Requires hospitalisation or prolongation of existing hospitalisation
- Results in persistent or significant disability or incapacity
- Is a congenital anomaly or birth defect
- Is another medically important condition

An important medical event that is not immediately life-threatening or will result in death or hospitalisation, but which may jeopardize the subject or may require medical intervention to prevent 1 of the outcomes listed above, should be reported as "serious" as well.

Adverse Event of Special Interest (AESI)

Adverse events of special interest are:

1. Adverse Events of Interest include urinary retention and withdrawal symptoms.
2. Adverse Events of Special Psychiatric Interest include nervousness, anxiety, panic attacks, insomnia, aggression, mania, suicidal ideation and development/worsening of depression.

Suicidal Adverse Event

Suicidal Adverse Events and Adverse Events suggestive of abuse potential will be recorded.

Adverse Events suggestive of abuse potential are the events listed in the FDA Guidance for Industry (see Appendix 6). In particular, the following AEs are defined as adverse events suggestive of abuse potential:

1. Euphoria-related terms (Euphoric mood; Elevated mood; Feeling abnormal; Feeling drunk; Feeling of relaxation; Dizziness; Thinking abnormal; Hallucination; Inappropriate affect)
2. Terms indicative of impaired attention, cognition, and mood (Somnolence; Mood disorders and disturbances)
3. Dissociative/psychotic terms (Psychosis; Aggression; Confusion and disorientation)
4. Related terms not captured elsewhere (Drug tolerance; Habituation; Drug withdrawal syndrome; Substance-related disorders)

The following special types of events should be recorded as AEs:

1. Pregnancy - Occurrence of pregnancy in a subject during a clinical study must be recorded.
2. Laboratory values that are outside the normal range and if, in the opinion of the Investigator, these values represent a clinically relevant change versus pre-treatment values are also defined as AEs.

12-lead ECG

All ECGs should be performed in a standardized method, in triplicate, and approximately 30 seconds apart, prior to blood draws or other invasive procedures. Each ECG must include the following measurements: ventricular rate, QRS duration, QT, corrected QT, RR, and PR intervals.

Physical examination

A full physical examination will include examination of general appearance, skin, neck (including thyroid), eyes, ears, nose, throat, heart, lungs, abdomen, lymph nodes, extremities, urinary system, musculoskeletal system, and nervous system, (including the central nervous system).

Psychiatric monitoring

The following psychiatric monitoring will be conducted at the screening visit and at each study visit:

1. suicide monitoring through the use of Columbia-Suicide Severity Rating Scale (C-SSRS)
2. monitor for depression symptoms through the use of the Beck Depression Inventory-II (BDI-II)
3. monitor for anxiety and sleep-related symptoms through the use of Beck Anxiety Inventory (BAI) and Pittsburgh Sleep Quality Index (PSQI)

In addition to the visit assessments detailed above, suicide monitoring using the C-SSRS will also be performed by a telephone contact with the subject 4 weeks post randomization (study day 42).

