Endpoints:	
Primary:
 
 Incidence and severity of AEs and Adverse Events of interest (urinary retention, withdrawal symptoms) over the course of the study. Adverse Events of special psychiatry interest (nervousness, anxiety, panic attacks, insomnia, aggression, mania, suicidal ideation, development/worsening of depression) over the course of the study Suicidal Adverse Events and Adverse Events suggestive of abuse potential (described in Section 6.2.2.3) will be analysed, and detailed narratives provided Haematology, chemistry, and urinalysis Actual change from end of the Screening Placebo Run-In Period in ECG readings and Week 8. ECG parameters of interest include: ventricular rate, QT interval, corrected QT interval, PR interval, and QRS duration Actual change from end of the Screening Placebo Run-In Period to each visit in standardised cuff systolic and diastolic blood pressure and radial heart rate 
Secondary:
 
The following Efficacy endpoints will be explored

	
 Percentage change from end of the Screening Placebo Run-In Period to Week 8 in the number of incontinence episodes/24 hours Absolute change from end of the Screening Placebo Run-In Period to Week 8 in the number of incontinence episodes/24 hours Proportion of subjects who become continent at Week 8 Change from end of the Screening Placebo Run-In Period in the number of incontinence pads used per week

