6.1.2.3 Responsibilities of the Investigator

Adverse event data should be obtained through observation of the subject, from any information volunteered by the subject, or through subject questioning. The general type of question asked could be similar to: "Do you have any health problems?" or "Have you had any health problems since your last clinic visit?"

Specific emphasis should be given to explore the occurrence of psychiatric events (nervousness, anxiety, panic attacks, insomnia, aggression, mania, suicidal ideation, development/worsening of depression). The patient should be routinely monitored by the C-SSRS, BDI-II, BAI and PSQI, as laid out in section 6.1.1.

If any patient experience suggestive suicidal ideation/behaviour as per the C-SSRS s/he will be submitted for psychiatric evaluation. The outcome of the psychiatric evaluation will determine the patient's suicidal state and whether the patient will continue in the study or prematurely withdrawn from participation.

Adverse Event terms such as euphoria, dissociative effects, hallucinosis, psychosis, impaired cognition, attention, mood and psychomotor effects, inappropriate affect, patient dropouts, overdoses, misuse and lost or unaccounted for medication and unjustified dose increases will result in detailed narratives, as they may be indicative of abuse potential.

Adverse events are to be documented/recorded accurately and completely on the AE pages of the respective eCRF and in the subject's source data.

All non-treatment and treatment-emergent AEs will be recorded. This is true even if the study drug was not administered according to study protocol.

For conditions leading to unplanned surgical procedures, the underlying condition, but not the procedure, should be documented as an AE.

Reporting Immediately Reportable Adverse Events (IRAEs):

For AEs that are “serious” (SAEs) additional separate documentation is required using the electronic SAE Forms.

The following variables will be recorded on the electronic SAE Form and on the eCRFs provided in accordance to the eCRF completion guidelines:

- Description of the event, including its duration (date of onset and resolution),
- Whether the event constitutes a SAE or not (if yes, see event seriousness criteria in [Section 6.1.2.1.2](#))
- Any action taken (eg, changes to study treatment, other treatment given, and follow up tests)
- Outcome of the event

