2.3 Primary Endpoint(s)

Safety:

1. Incidence and severity of AEs and Adverse Events of interest (urinary retention, withdrawal symptoms) over the course of the study. AEs are recorded at visits 2,3,4,5,6 and 7.
2. Adverse Events of special psychiatry interest (nervousness, anxiety, panic attacks, insomnia, aggression, mania, suicidal ideation, development/worsening of depression) over the course of the study
3. Suicidal Adverse Events and Adverse Events suggestive of abuse potential will be analysed, and detailed narratives provided
4. Lab parameters: Haematology and chemistry recorded at visit 1,2,6 and 7. Urinalysis recorded at visit 1 and 2.
5. Absolute change from end of the Screening Placebo Run-In Period in ECG readings and Week 8 (Visit 6). ECG parameters of interest include: ventricular rate, QT interval, corrected QT interval, PR interval, and QRS duration
6. Absolute change from end of the Screening Placebo Run-In Period to each visit in standardised cuff systolic and diastolic blood pressure and radial heart rate

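### The SAP's list of abuse-potential events names none of the drug-handling signals that the protocol singles out, and two of them have no dedicated output

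*SAP*

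**What the plan says.** The endpoint appears in both documents. SAP section 2.3, item 3, under the primary endpoints, reads: "Suicidal Adverse Events and Adverse Events suggestive of abuse potential will be analysed, and detailed narratives provided". Protocol section 8.7.1 lists the same item, and the protocol synopsis lists it as primary with a pointer: "Adverse Events suggestive of abuse potential (described in Section 6.2.2.3) will be analysed".

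The protocol has no Section 6.2.2.3; section 6.2 holds only 6.2.1, on the bladder diary. The text that matches is in section 6.1.2.3. It starts with psychiatric and cognitive terms, includes psychomotor effects, and ends: "inappropriate affect, patient dropouts, overdoses, misuse and lost or unaccounted for medication and unjustified dose increases will result in detailed narratives". The reason it gives is that these may point to abuse potential.

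SAP section 5.3 first refers to an FDA guidance, which Appendix 6 gives as a citation only. It then continues "In particular, the following AEs are defined as adverse events suggestive of abuse potential" and sets out four groups: euphoria-related terms; impaired attention, cognition and mood; dissociative or psychotic terms; and a residual group of drug tolerance, habituation, drug withdrawal syndrome and substance-related disorders.

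SAP section 6.7, item 3, tabulates these events by system organ class, preferred term and arm, with Clopper-Pearson 95% intervals.

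SAP section 5.2 derives capsules taken as dispensed, minus returned, minus "capsules not taken/not returned".

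**The concern.** An endpoint listed as primary has its content narrowed between protocol and SAP, and the SAP's own list of departures from the protocol (section 1.5) does not mention it. The items left out are those about how subjects handle the drug: taking too much, misusing it, losing it, or raising the dose without justification. Both documents justify their choice of safety parameters partly by attention to events indicative of abuse potential (Protocol 3.2, SAP 1.6).

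Two things are at stake. A reader of the abuse-potential table would take it as the full answer to the protocol's question, although it rests on a shorter list. Narratives written to Protocol 6.1.2.3 and a table built on SAP 5.3 would also cover different sets of subjects, with nothing in the plan to explain the difference.

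**Working it through.** The documents state no figure to reproduce. The check is a comparison of texts, item by item.

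| Item named in Protocol 6.1.2.3 | Named in SAP 5.3 list? | Where else the SAP would show it |
|---|---|---|
| Psychomotor effects | No | General TEAE tables, if recorded as an AE |
| Patient dropouts | No | Withdrawals by reason and arm (SAP 6.4, 6.8), not linked to abuse potential |
| Overdoses | No | Defined and classed as immediately reportable (SAP 5.3), but 6.7 and 6.8 plan no overdose or immediately-reportable table; TEAE tables if entered as an AE |
| Misuse | No | TEAE tables if entered as an AE |
| Lost or unaccounted-for medication | No | Only as a term inside the compliance formula (SAP 5.2) |
| Unjustified dose increases | No | No dedicated output |

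Result: 0 of 6 items are named. One (dropouts) is fully tabulated elsewhere. Three (psychomotor effects, overdose, misuse) depend on AE entry; coding under substance-related disorders might also bring some overdose or misuse terms into the abuse table. Two (unaccounted-for medication, unjustified dose increases) have no dedicated output.

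**Compliance as a fallback.** Let D be capsules dispensed, R returned, and U capsules missing at the count.

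- If U is entered as not taken/not returned: capsules taken = D − R − U. The missing capsules are treated as not swallowed, and compliance falls.
- If U is not entered there: capsules taken = D − R. The missing capsules count as swallowed, and compliance rises, possibly above 100%.

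The same missing capsules can therefore move compliance either way, depending on how the site fills in the form. Because one field merges not taken with not returned, the compliance summary cannot stand in for a count of unaccounted-for medication.

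**Scale, as an illustration only.** The documents give no expected rate, so the counts k below are assumed.

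- Input: about 78 randomised at 2:1 (SAP 3.1), so litoxetine n = 78 × 2/3 = 52.
- Method: Clopper-Pearson, as the SAP specifies. Lower limit = Beta quantile 0.025 with parameters (k, n − k + 1); upper limit = Beta quantile 0.975 with parameters (k + 1, n − k).
- Suppose k litoxetine subjects have only a drug-handling event that falls outside the SAP list, and no other abuse-potential event occurs in that arm.

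| k | Table on SAP 5.3 list | Table with the protocol's items added |
|---|---|---|
| 1 | 0/52 = 0% (0 to 6.8%) | 1/52 = 1.9% (0.05 to 10.3%) |
| 3 | 0/52 = 0% (0 to 6.8%) | 3/52 = 5.8% (1.2 to 16.0%) |
| 5 | 0/52 = 0% (0 to 6.8%) | 5/52 = 9.6% (3.2 to 21.0%) |

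**The case against.** The best defence has five parts.

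1. **Section 6.1.2.3 is a narrative trigger.** It sits among investigator responsibilities and says these items lead to narratives. It does not say that they define the endpoint. SAP 2.3 keeps the narratives, nothing in the SAP cancels the trigger, and narratives may cover more than a table. This stands as a reading of the wording. But the synopsis says the events are described elsewhere in the protocol, and 6.1.2.3 is the only text there that does so.

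2. **The SAP list may not be closed.** The general rule points to an external guidance, and substance-related disorders could take in some misuse or overdose terms. This stands: the exclusion is not absolute. The guidance content is not in the documents, so it cannot be relied on either way.

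3. **Other outputs catch some of these items.** A reader might infer that drug-handling signals are never counted, or that the trial could not report an overdose or misuse. The documents do not support that: withdrawals are summarised by reason and arm, and an overdose or misuse entered as an AE reaches the TEAE tables with intervals by arm. A reader might also infer that extra capsules always show up as lower compliance. That is not so either, because capsules recorded as taken raise it.

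4. **The endpoint's weight is mixed.** SAP 6.7 calls the overall TEAE analysis the primary safety endpoint, although SAP 2.3 lists abuse-potential events under the same primary heading. This tempers the importance of the point; the mismatch remains.

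5. **Adding every dropout would swamp the table.** At the planned 30%, about 0.30 × 78 = 23 subjects would enter it. This stands, and the fix below leaves dropouts where they are.

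**Conclusion.** The point holds in a limited form and is worth fixing. Followed as written, the SAP does not explicitly count overdose, misuse, unaccounted-for medication, unjustified dose increases, dropouts or psychomotor effects as abuse-potential events, although the protocol names all six as possibly indicative of abuse, and the narrowing is not disclosed. The gap is widest for unaccounted-for medication and unjustified dose increases, which have no dedicated output. It is smaller for overdose, misuse and psychomotor effects, which depend on AE entry and coding, and smallest for dropouts, which are tabulated but not tied to the required narratives.

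The size in subjects cannot be derived from the documents. The figures of 1, 3 or 5 in 52 are assumptions that show what a table could miss; they are not forecasts. The conclusion also assumes that Protocol 6.1.2.3 is the intended target of the synopsis cross-reference, and that the four groups in SAP 5.3 are applied as the working list.

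**What to change.** - **SAP 5.3 and 6.7 item 3:** add overdose, misuse, unaccounted-for medication, unjustified dose increase and psychomotor terms. Name the existing source for each: the AE pages and overdose reports (Protocol 6.1.2.3, 6.1.2.6.1), and drug accountability (Protocol 5.5 and the visit procedures in 7.1). Report the number and percentage of subjects by arm, with narratives. Items that are not coded AEs need their own rows outside the system organ class and preferred term layout.
- **SAP 5.2:** where the eCRF allows, report unreturned capsules separately from capsules not taken.
- **Dropouts:** keep them in the disposition table and cross-reference them to the narratives that Protocol 6.1.2.3 requires. Do not add all dropouts to the abuse table.
- **Protocol synopsis:** change the cross-reference from 6.2.2.3 to 6.1.2.3.
- **SAP 1.5:** state and justify any narrowing that remains.

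The cost is some wording and one extra table from data the protocol already requires. The downside is that some counts will be non-specific, for example capsules lost innocently, so the table should be read with the narratives.
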